6. STATISTICAL METHODOLOGY AND ANALYSES

6.1 GENERAL CONSIDERATIONS

Standard statistical methods will be employed to analyze all data. It is anticipated that the following techniques may be used: paired t-test; independent two-sample t-test; ANOVA; chi-square test; and Fisher's exact test. Assumptions of normality will be tested using the Shapiro-Wilk test. If distributional assumptions are violated, non-parametric techniques, such as the Wilcoxon signed-rank test, Wilcoxon rank-sum test, and Kruskal-Wallis test, will be employed. Summaries for quantitative variables will include the sample size, mean, median, standard deviation, minimum, and maximum. Summaries for categorical variables will include the number and percent of patients for each outcome. Statistical significance will be declared if the two-sided p-value is ≤ 0.05 . Additional statistical analyses, other than those described in this SAP, may be performed if deemed appropriate.

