13. STATISTICAL METHODS

13.1 Determination of Sample Size

Up to 60 female subjects, 20 per dose arm, meeting the inclusion/exclusion criteria will be randomized in a 1-1-1 fashion. The sample size was powered based on the two-sample t-test that will be used to make pairwise comparisons between treatment groups.

a sample of 18 subjects per group would provide 80% power to detect a statistically significant difference between the treatment groups.

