13.2.2.5 BBSS Patient Reported Scores

The percent change from baseline in each of the daily average combined BBSS patient-reported scores (dysmenorrhea, dyspareunia and non-menstrual pelvic pain) will be analyzed to compare the baseline menstrual cycle to a similar period leading up to the last day of dosing in Cycle 1 (Week 18). An overall comparison among the 3 treatment groups will be performed using a one-way Analysis of Covariance, including baseline BBSS score and treatment in the model. Pairwise comparisons of the treatment groups will be made using a two-sample t-test. While the primary assessment will be based on Visit 12 (after 18 weeks of treatment) summaries will also be prepared for each of the other visits. [REDACTED]

The BBSS patient scores during the active treatment stage of the study (stage 3) will also be summarized

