13.2.2.7 VAS Assessment of Pain

The percentage change from baseline VAS pain score will be analyzed within treatment group and between treatment groups. An overall comparison among the 3 treatment groups will be performed using a one-way Analysis of Variance. Pairwise comparisons of the treatment groups will be made using t-test or non-parametric test as appropriate. While the primary assessment will be based on scores at Visit 12 (after 18 weeks of treatment), summaries will also be prepared for each of the other visits. If data are missing, a last observation carried forward procedure will be used, including the baseline, if necessary.

The VAS pain scores collected during the active treatment stage of the study (Stage 3) will also be summarized.

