6.7.5 BBSS Patient Reported Scores

Patient reported daily BBSS component scores (dysmenorrhea, pelvic pain, dyspareunia) and total score and the change from baseline in each will be summarized from patient diaries.

The statistical significance of the change from baseline within treatment groups will be based on a paired t-test or Wilcoxon signed-rank test, as appropriate. The change from baseline will be compared between groups using a t-test or Wilcoxon rank-sum test, as appropriate.

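### The SAP lets a Shapiro-Wilk result choose between t-test and rank-sum test, so the test and its hypothesis depend on the data and can differ between the two doses

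*SAP*

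**What the plan says.** Protocol section numbers below refer to the last protocol version in the file.

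- **SAP 6.1** sets the pre-test ("Assumptions of normality will be tested using the Shapiro-Wilk test") and its consequence: "If distributional assumptions are violated, non-parametric techniques, such as the Wilcoxon signed-rank test, Wilcoxon rank-sum test, and Kruskal-Wallis test, will be employed". It gives no significance level for the pre-test. It does not say whether the test is applied to each arm, to each pair of arms, to residuals, or once to all three arms.
- **SAP 6.7.5**, patient-reported BBSS: "The change from baseline will be compared between groups using a t-test or Wilcoxon rank-sum test, as appropriate". Sections 6.7.3, 6.7.4, 6.7.6 and 6.7.7 use the same formula for analgesic use, daily pain and sexual avoidance, physician BBSS and VAS.
- **Protocol 13.2.2.5**, patient-reported BBSS, specifies a "one-way Analysis of Covariance, including baseline BBSS score and treatment in the model", followed by: "Pairwise comparisons of the treatment groups will be made using a two-sample t-test". Sections 13.2.2.1 to 13.2.2.3 fix the same pair of methods for prescription, over-the-counter and overall analgesic use.
- **Protocol 13.1**: "The sample size was powered based on the two-sample t-test that will be used to make pairwise comparisons between treatment groups". SAP 3.2 repeats this sentence.
- **Protocol 13.2.2.7**, VAS, leaves the choice open: "Pairwise comparisons of the treatment groups will be made using t-test or non-parametric test as appropriate". Section 13.2.2.8 does the same for the NRS.

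**The concern.** A fixed test asks one question. The t-test compares mean changes. The rank-sum test responds to any tendency of one arm to lie above the other, and differences in spread and shape affect it. Under the SAP, the question asked about the primary endpoint is settled only after the outcome data have been seen. Nothing requires the answer to be the same for 6 mg and 12 mg.

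Unequal shapes are plausible here. SAP 5 counts women who become amenorrheic, which could push dysmenorrhea to its floor in some treated women only. Protocol 8.2.1 lets women stop for lack of efficacy after 28 days, and 13.2.2 imputes no change where post-baseline data are missing. Both could put unequal spikes at zero in the arms.

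At stake is the reading of a two-dose phase 2 trial. A t-test p-value for one dose beside a rank-sum p-value for the other does not compare like with like. The SAP also departs, without saying so, from the test that the protocol names and that SAP 3.2 says the trial was powered on.

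**Working it through.** **1. The plan's own figure.** Protocol 13.1 states 18 per group for 80% power. The effect and SD are not in the public text, so the figure cannot be reproduced. Solving backwards, which is no check, gives a standardised difference of (1.960 + 0.842) × √(2/18) = 0.93, or 0.96 with the exact noncentral t. Nothing below depends on it.

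**2. How often the two doses get different tests, by formula.** Assume a pre-test at 0.05 in each arm, with a comparison going to rank-sum if either of its arms fails. Let p be the chance that an arm fails, the same in all three arms. The tests differ only if placebo passes and exactly one dose arm fails:

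P(different) = (1 − p) × 2p(1 − p) = 2p(1 − p)²

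At n = 20, simulated values of p are 5% (normal), 31% (skewness 1) and 58% (skewness 1.5).

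- Normal: 2 × 0.05 × 0.95² = 9.0%
- Skewness 1: 2 × 0.31 × 0.69² = 29.5%
- Skewness 1.5: 2 × 0.58 × 0.42² = 20.5%

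The maximum is at p = 1/3: 2 × (1/3) × (2/3)² = 8/27 = 29.6%. If placebo is normal and only the dose arms are skewed (failure chance q), the formula becomes 0.95 × 2q(1 − q). That gives 40.6% at q = 0.31 and 46.3% at q = 0.58.

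**3. Simulation under three readings of the rule.** Three arms of 20, 20,000 runs (standard error about 0.15 points), pre-test at 0.05, pooled t-test if passed and rank-sum if failed. The distributions are assumed and identical in all arms. All figures are percentages.

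| Shape | Type I error, fixed t | Type I error, SAP rule (range over readings) | Different tests: per arm | Different tests: pair residuals | Different tests: one decision for all arms |
|---|---|---|---|---|---|
| Normal | 5.3 | 5.4-5.5 | 9.0 | 8.1 | 0 |
| Gamma, skewness 1 | 4.9 | 5.4-5.6 | 29.6 | 34.2 | 0 |
| t, 3 df | 4.7 | 4.9-5.3 | 29.1 | 34.0 | 0 |
| 40% spike at zero | 5.0 | 4.9-5.7 | 16.8 | 25.6 | 0 |
| Exponential | 4.7 | 4.9-5.1 | 4.3 | 3.6 | 0 |
| Lognormal | 3.9 | 5.0 | 0.9 | 0.7 | 0 |

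A fixed rank-sum test has error 4.8-5.2% over these shapes. With 18 per arm (8,000 runs) the rule gives 4.7-5.6%.

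**4. Why the error hardly moves.** Among exponential samples that pass the pre-test, the t-test rejects in 13.0%, but only 2.5% of comparisons pass: 0.025 × 0.130 + 0.975 × 0.048 = 5.0%. For lognormal data: 0.005 × 0.212 + 0.995 × 0.0493 = 5.0%.

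**5. Equal means, unequal shapes.** Rejection rates in percent, n = 20:

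| Placebo and active | Fixed t | Fixed rank-sum | SAP rule |
|---|---|---|---|
| Normal and exponential | 5.3 | 7.1 | 7.0-7.3 |
| Normal and lognormal | 8.3 | 21.2 | 20.3-21.2 |
| Skewed active arm, 1.5 × placebo SD | 5.4 (Welch) | 8.6 | 9.0 |
| Skewed active arm, 2 × placebo SD | 5.7 (Welch) | 12.5 | 12.6 |

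The last two rows combine separate simulation runs. The SAP rule tracks the fixed rank-sum test throughout, so the excess comes from that test's different hypothesis and not from the pre-test.

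**The case against.** A reader might infer that the pre-test breaks the 5% level. The figures do not support this. When the arms share a distribution, the rule stays within about 0.7 points of 5%. When only the means are equal, a fixed rank-sum test rejects almost as often, and the arms really do differ.

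A reader might also infer that the two doses will be tested differently. The SAP does not say so. It is silent on the unit of testing, and a single decision across arms would remove the problem.

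Nor are the dose results unreadable side by side. SAP 6.1 requires means, medians and SDs whichever test is used, so it is the p-values that lose comparability.

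Other parts of the defence stand. For VAS the SAP follows the protocol's own open wording. No bleeding or NRS analysis is visible in the public SAP, so no conflict can be shown there. Protocol 13.3 says the p-values serve to quantify differences because the trial was not powered for efficacy, although 13.1 claims 80% power. That limits the consequences but does not remove the point: p-values from two different tests quantify different things, and SAP 6.1 still says "Statistical significance will be declared if the two-sided p-value is ≤ 0.05".

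**Conclusion.** The point holds as a prespecification gap. For patient-reported BBSS and analgesic use, the SAP replaces a test fixed in the protocol with a data-driven choice between two tests of different hypotheses. It has no rule keeping both doses on one test.

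Different tests for the two doses would occur in about 9% of trials with normal data and 20-30% with moderately skewed data, if the pre-test is applied per arm at 0.05. Residuals within each pair give similar or somewhat different rates, and one decision for all three arms gives 0%. The level, the unit and the outcome distributions are assumptions, because the documents give none of them. The protocol's ANCOVA was not simulated.

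The effect on per-comparison type I error is small. The change is worth making because it settles the primary hypothesis in advance at the cost of wording.

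**What to change.** Before unblinding, delete the Shapiro-Wilk rule and the words *as appropriate* from SAP 6.1 and 6.7.3 to 6.7.7. Name one primary between-arm test per endpoint, used for both doses.

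- **BBSS and analgesic use:** the treatment contrast from the protocol's baseline-adjusted ANCOVA, or a two-sample t-test in Welch form.
- **VAS and NRS:** name one test, since the protocol leaves the choice open.
- **Every endpoint:** report the rank-sum test for both doses as a fixed sensitivity analysis, whatever the data look like.

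Making the rank-sum test primary for pill counts would depart from Protocol 13.2.2.1 to 13.2.2.3 and would have to be recorded as such.

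The cost is SAP wording, plus some loss of power if the realised data are strongly skewed. The change does not deal with the two unadjusted dose comparisons (SAP 6.2). With one fixed test, the chance of at least one false positive over both doses is still 7.0-9.4%, against 1 − 0.95² = 9.75% for independent tests.

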6.2 ADJUSTMENT FOR MULTIPLE COMPARISONS

No adjustments for multiple comparisons will be made.

6.3 EXTENT OF EXPOSURE

The duration of exposure will be calculated for each subject. Summary statistics will be presented using the Intent-to-Treat population.

6.4 SUBJECT DISPOSITION

Subject disposition will be summarized in terms of the number of subjects who completed the study and discontinued early from the study. Disposition will be summarized using the Intent-to-Treat population.

6.5 DEVIATIONS

The total number of each deviation type will be summarized for the Intent-to-Treat population.

6.6 DEMOGRAPHIC AND BASELINE CHARACTERISTICS

Demographic and baseline characteristics will be summarized for the Intent-to-Treat population. Results will be presented for each treatment group.

6.7 EFFICACY ANALYSES

Efficacy analyses will be conducted using the Intent-to-Treat population, as defined in Section 4.1.

6.7.3 Analgesic Use

Analgesic use (number of pills) and change/percentage change from baseline will be summarized from patient diaries. Non-prescription, prescription, and total analgesic use will be analyzed.

The statistical significance of the change/percentage change from baseline within treatment groups will be based on a paired t-test or Wilcoxon signed-rank test, as appropriate. The change/percentage change from baseline will be compared between groups using a t-test or Wilcoxon rank-sum test, as appropriate.

6.7.4 Patient Reported Daily Endometriosis Pain and Sexual Avoidance Scores

Patient reported daily endometriosis pain and sexual avoidance scores and the change from baseline in each will be summarized from patient diaries.

The statistical significance of the change from baseline within treatment groups will be based on a paired t-test or Wilcoxon signed-rank test, as appropriate. The change from baseline will be compared between groups using a t-test or Wilcoxon rank-sum test, as appropriate.

6.7.5 BBSS Patient Reported Scores

Patient reported daily BBSS component scores (dysmenorrhea, pelvic pain, dyspareunia) and total score and the change from baseline in each will be summarized from patient diaries.

The statistical significance of the change from baseline within treatment groups will be based on a paired t-test or Wilcoxon signed-rank test, as appropriate. The change from baseline will be compared between groups using a t-test or Wilcoxon rank-sum test, as appropriate.

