Study Endpoints	
The study endpoints will be:
 
Primary Endpoint
 
• Change and percent change in the individual BBSS scores of the three patient reported outcomes (dysmenorrhea, dyspareunia and non-menstrual pelvic pain) by study visit and treatment cycle. 
Secondary Endpoints
 
• Change in daily average use and percent change of prescription medications from the baseline menstrual cycle to the matching period leading up to Week 18, the last day of dosing of the first cycle of treatment.• Change in daily average use and percent change of over the counter medications from the baseline menstrual cycle to the matching period leading up to Week 18, the last day of dosing of the first cycle of treatment, calculated based on days with reported values.• Change in daily average use and percent change of overall medication use, prescription and over the counter, from the baseline menstrual cycle to the matching period leading up to Week 18, the last day of dosing of the first cycle of treatment, calculated based on days with reported values.• Change and percent change in BBSS score incorporating the two physician reported scores by study visit and treatment cycle.• Change from baseline in pain assessed using a Visual Analog Scale (VAS) by study visit and treatment cycle.• Change from baseline in daily average dysmenorrhea and non-menstrual pelvic pain using an 11-point numerical rating scale (NRS) by study visit and treatment cycle.
Statistical Methods:	A Statistical Analysis Plan (SAP) will be developed prior to unblinding of the data that will outline all planned analyses and

[figure not shown]
analysis populations. The first efficacy analysis will be conducted when all subjects complete the first cycle of treatment. A second analysis will summarize the subject's additional treatment cycles which will be conducted after all subjects complete study treatment and follow-up.

[figure not shown]
Summaries for quantitative variables include the sample size, mean, median, standard deviation, minimum, and maximum. Summaries for categorical variables include the number and percent of patients for each outcome. All summaries will be prepared for each treatment group.

[figure not shown]
Summaries will be prepared for each treatment group of subject accountability, baseline demographic, and medical history data.

[figure not shown]

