Continuous efficacy endpoints, such as the percentage change from baseline in the use of prescription medications, will assess treatment effect using an Analysis of Covariance, including the baseline prescription medication usage and treatment in the model. Pairwise comparisons between treatment groups will be made using a two-sample t-test. Other continuous efficacy variables will be treated similarly.

[figure not shown]

[figure not shown]
[figure not shown]

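### In the visible text no dose-versus-placebo comparison adjusts for baseline. This is valid but usually less precise, and the documents disagree on ANCOVA for VAS and NRS and on the overall three-group test.

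*SAP*

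**What the plan says.** References to the protocol are to its last full text in the file, taken to be Amendment 9, which the SAP says it follows.

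- **Protocol synopsis, Statistical Methods.** Continuous efficacy endpoints "will assess treatment effect using an Analysis of Covariance, including the baseline prescription medication usage and treatment in the model". Pairwise comparisons are two-sample t-tests. It then adds: "Other continuous efficacy variables will be treated similarly". The listed endpoints include "Change from baseline in pain assessed using a Visual Analog Scale (VAS) by study visit and treatment cycle", and a matching NRS endpoint.
- **Protocol 13.1.** "The sample size was powered based on the two-sample t-test that will be used to make pairwise comparisons between treatment groups". The visible result is 18 per group for 80% power, with up to 20 per arm randomized.
- **Protocol 13.2.2.5 (patient-reported BBSS, the primary endpoint).** The overall three-group comparison is made "using a one-way Analysis of Covariance, including baseline BBSS score and treatment in the model". Then: "Pairwise comparisons of the treatment groups will be made using a two-sample t-test". Sections 13.2.2.1 to 13.2.2.4 and 13.2.2.6 follow the same pattern.
- **Protocol 13.2.2.7 (VAS).** "An overall comparison among the 3 treatment groups will be performed using a one-way Analysis of Variance". Section 13.2.2.8 (NRS) says the same. Pairwise tests for both are a t-test or a non-parametric test.
- **SAP 6.7.5.** "The change from baseline will be compared between groups using a t-test or Wilcoxon rank-sum test, as appropriate". Sections 6.7.3, 6.7.4, 6.7.6 and 6.7.7 use the same choice of test, on change, percentage change or both.
- **SAP 6.1.** The list of techniques that may be used includes t-tests, ANOVA, Shapiro-Wilk and rank tests. ANCOVA is not on it.

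**The concern.** The dose-versus-placebo contrasts are what this study is sized for and what a reader will take from it. Each subject's baseline is recorded over a full menstrual cycle, yet it enters those contrasts only by subtraction or division. With about 20 women per arm, chance baseline differences are not small: the difference between two arm means has SD sqrt(2/20) = 0.316 baseline SDs and exceeds 0.3 SD with probability 0.34. A change score over- or under-corrects for such a difference unless the regression slope of follow-up on baseline equals 1. The usual cost is a wider interval than the same data could give.

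The second matter is which analysis is planned. A programmer working from the visible SAP would produce no ANCOVA and no three-group test. One working from Protocol 13.2.2 would produce both, with ANOVA for VAS and NRS. One working from the synopsis would expect ANCOVA for those two as well.

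**Working it through.** **1. The texts side by side**

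| Source | Overall three-group test | Pairwise test |
|---|---|---|
| Synopsis | ANCOVA; other continuous variables alike | t-test, no covariate |
| Protocol 13.2.2.1 to 13.2.2.6 | ANCOVA with baseline | t-test, no covariate |
| Protocol 13.2.2.7 and 13.2.2.8 | one-way ANOVA | t-test or non-parametric, no covariate |
| SAP 6.7.3 to 6.7.7 (visible) | none stated | t-test or rank-sum, no covariate |

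The pairwise column agrees throughout in having no covariate. The disagreements are in the overall column: VAS and NRS within the protocol, and all visible endpoints between protocol and SAP.

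**2. The plan's own figure**

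The effect and SD behind 18 per group are not visible, so the figure cannot be reproduced, only inverted. For a two-sample t-test with two-sided 0.05, n = 18 per group (34 df) and 80% power, the noncentral t gives a standardized difference d = 0.961, in SDs of change. At 20 per arm the same d gives 84.2% power.

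**3. Effect of adjusting**

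The visible documents give neither of the following, so both are assumed: r, the baseline/follow-up correlation, and k, the follow-up SD divided by the baseline SD. Taking baseline SD as 1:

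- Variance of change: 1 + k² − 2rk
- Residual variance after ANCOVA: k²(1 − r²)
- Ratio: V = k²(1 − r²)/(1 + k² − 2rk), which is (1 + r)/2 when k = 1
- Expected cost of chance baseline imbalance in two arms of n: factor 1 + 1/(2n − 4), which is 1 + 1/32 at n = 18
- Power: noncentral t with 2n − 3 df and effect d/sqrt(V(1 + 1/(2n − 4)))

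Example with k = 1, r = 0.5, n = 18: V = 0.75; 0.75 × 1.03125 = 0.773; effect 0.961/0.879 = 1.093; noncentrality 1.093 × sqrt(18/2) = 3.28 on 33 df; power 88.9%. The interval-width ratio is 0.879 × 2.0345/2.0322 = 0.880.

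| k = 1 | r = 0.3 | 0.5 | 0.7 | 0.9 |
|---|---|---|---|---|
| V | 0.65 | 0.75 | 0.85 | 0.95 |
| Power, n = 18 (t-test 80.0%) | 92.8% | 88.9% | 84.8% | 80.7% |
| Interval width ratio, n = 18 | 0.820 | 0.880 | 0.937 | 0.991 |
| Power, n = 20 (t-test 84.2%) | 95.2% | 92.1% | 88.6% | 85.0% |

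At n = 18 with unequal SDs:

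- k = 1.5: power 84.0%, 80.2%, 78.8% and 87.8% for the same four r.
- k = 0.7: power 97.6% to 99.1%.
- rk = 1 (slope 1, V = 1): power 78.7%, interval 1.7% wider. This is the worst case, a loss of about 1.3 points.

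These figures apply to t-tests on absolute change (SAP 6.7.4 to 6.7.6 and part of 6.7.3). They do not cover percentage change (Protocol 13.2.2.5, SAP 6.7.7, part of 6.7.3) or rank-sum tests.

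**4. Type I error, and which ANCOVA**

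Simulation used 40,000 trials per cell, three arms of 18, r = 0.3, 0.5 and 0.7, equal means, and assumed follow-up SDs (placebo/dose A/dose B) of 1/1/1, 1/0.7/0.7, 1/0.7/0.5 and 1/0.5/0.3.

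| Method | Type I error |
|---|---|
| Planned t-test | 0.048 to 0.052 |
| Two-arm ANCOVA | 0.047 to 0.056 |
| Three-arm ANCOVA, HC3 errors | 0.043 to 0.050 |
| Three-arm ANCOVA, pooled variance, equal SDs | 0.049 to 0.050 |
| Same, unequal SDs | 0.058 to 0.098 |

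Unequal spread is plausible here. SAP section 5 counts subjects becoming amenorrheic as an efficacy endpoint, so scores on active drug may be compressed.

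**The case against.** The best reply is that the sponsor planned unadjusted pairwise t-tests openly, sized the study on them, and repeated them in the synopsis, Protocol 13.2.2 and the SAP. No document promises a covariate-adjusted dose-versus-placebo contrast. That stands: on the pairwise tests the SAP's t-test does not depart from the protocol, and a reader who infers an error there goes beyond the text.

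A reader might also infer that the synopsis, Protocol 13.2.2 and the SAP describe three different analyses. They do not. The synopsis and 13.2.2 share one scheme and part only on VAS and NRS, which are secondary endpoints, and that conflict rests on one loosely worded synopsis sentence.

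Nor can one say that the SAP leaves the missing ANCOVA unexplained. SAP 6.7.1 and 6.7.2 and any NRS section are not visible, SAP 3.2 breaks off, Protocol 13.2.2.4 and 13.2.2.5 have redactions after the test description, and SAP 6.1 lists only what may be used. Since that list includes ANOVA and Kruskal-Wallis, three-group tests may be intended.

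The data-driven choice between t-test and rank-sum showed no harm to type I error: 0.047 to 0.052 in a simulation with lognormal data and 18 per arm. Fixing the rank test's role in advance is for clarity about which result counts.

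Finally, Protocol 13.3 says the study was not powered for efficacy hypotheses and that p-values serve to quantify treatment differences. That lowers the urgency. It does not remove the point, because a tighter interval serves that same purpose.

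**Conclusion.** The point holds as a cheap improvement plus a reconciliation of wording. The planned comparisons are valid, and what they give up is precision. Under equal SDs the gain from adjusting is about 13, 9, 5 and 1 points of power at 18 per group for r = 0.3, 0.5, 0.7 and 0.9 (92.8, 88.9, 84.8 and 80.7 minus 80.0). At 20 per arm it is about 11, 8, 4 and 1 points. Across the SD ratios examined, the range runs from a loss of about 1.3 points to a gain of about 19. All of this rests on assumed r and k, on an effect size inverted from the stated power, and on absolute change analysed by t-test.

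The two inconsistencies need no assumption about numbers. VAS and NRS have ANOVA in 13.2.2.7 and 13.2.2.8 against the synopsis. The overall three-group comparison and ANCOVA are absent from visible SAP 6.7.3 to 6.7.7, although the SAP says it adheres to Amendment 9. Whether hidden text resolves the second cannot be known.

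**What to change.** 1. In SAP 6.7.3 to 6.7.7, for each endpoint, make the leading dose-versus-placebo estimate the ANCOVA-adjusted difference in absolute change, with treatment and that endpoint's own baseline as terms, reported with a 95% interval. Fit it on the two arms compared, or use HC3 standard errors if all three arms are modelled. Do not use a pooled three-arm error variance. Absolute change is already among the listed endpoints, for VAS and NRS too.
2. Label the planned percentage-change t-tests and the rank-based tests as supportive, and fix the rank test's role in advance. SAP 6.2 makes no multiplicity adjustment, so it must be clear which result leads.
3. Restore the protocol's overall three-group ANCOVA in the SAP, or state that it is dropped and why. Align the synopsis with Protocol 13.2.2.7 and 13.2.2.8 on ANCOVA or ANOVA for VAS and NRS.

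Cost: wording and a few lines of code, with no new data. Downsides: one degree of freedom; a linearity assumption, to be checked by plotting residuals against baseline; up to about 1.3 points of power when rk is near 1; and roughly 1 to 3 further points if HC3 errors are used.
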